7.8 Appropriateness of test items

Efficacy endpoints chosen in this study are similar to those in the preceding study in order to study and examine various aspects of long-term efficacy.

Safety endpoints chosen in this study are also similar to that in the preceding study.

7.9 Permitted range of test times

Examination, observation and tests will be performed in accordance with Appendix 1. If performance at the date and time shown in Appendix 1 is impossible, for unavoidable reasons, performance within the

permitted range shown in Table 7-3 will be acceptable. Data collected outside the permitted range will be taken to be missing for that visit. When the dose is to be increased from 20 to 40 mg/day, or from 40 to 60 mg/day for the first time, the pre-increase dose must be administered for at least 7 days.

Table 7-3. Permitted range of time of examinations, observations and tests

	Visit	Week	Stipulated date of visit	Permitted range (days)	Range (Day)
Screening period	1	-3 to -1	-21 to -7	-	-
Treatment period	2	0	0 (Registration)	0	-
	3	1	7	±3	4 to 10
	4	2	14	±3	11 to 17
	5	4	28	±7	21 to 35
	6	8	56	±7	49 to 63
	7	12	84	±7	77 to 91
	8	16	112	±7	105 to 119
	9	20	140	±7	133 to 147
	10	24	168	±7	161 to 175
	11	28	196	±7	189 to 203
	12	32	224	±7	217 to 231
	13	36	252	±7	245 to 259
	14	40	280	±7	273 to 287
	15	44	308	±7	301 to 315
	16	48	336	±7	329 to 343
	17	50	350	±3	347 to 353
	At discontinuation	-	Date of final administration in treatment period	+3	-
Tapering period	18	51 If the last dose is 40 mg	On Day 7, taking Visit 17 (or the time of discontinuation during the treatment period) to be Day 0.	±3	-
		52 If the last dose is 60 mg	On Day 14, taking Visit 17 (or the time of discontinuation during the treatment period) to be Day 0.	±3	-
	At discontinuation	-	Final administration in tapering period	+3	-
Follow-up period	19	52 to 53	On day 7 or later, taking the final administration date to be day 0.		-

8. Statistical analysis

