3.3.1 Study period for each subject

Up to a total of 56 weeks, consisting of a 1- to 3-week screening period, a 50-week treatment period, a 1- to 2-week tapering period, and a 1-week follow-up period.

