7.7.2 Columbia Suicide Severity Rating Scale (C-SSRS)

At Visits 1 (or Visit 2 for consecutive subjects) to 18 (or discontinuation of the treatment or tapering period), the principal investigator or sub-investigator will evaluate suicidal thinking using a questionnaire. For consecutive subjects, a measurement at Visit 9 in the preceding study may be used as a measurement at Visit 2 of this study. The date and results of evaluation will be recorded in the CRF. The principal investigator or sub-investigator will judge whether any abnormal change from baseline (Visit 2) is clinically significant (refer to Section 7.7.7.7) and will record any changes judged to be clinically significant as adverse events.

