6.3 Assessments, observations and tests: Permitted timing and handling in statistical analyses

In principle, data obtained at the time-points shown in the case report forms, and collected in accordance with the performance schedule shown in the study protocol, will be used for the statistical analysis. In the case of data reported at the discontinuation visit, the time-points for use in analyses will be determined on the basis of the permitted ranges in the performance schedule. If there is duplication by data obtained at the scheduled visits and data obtained at the discontinuation tests, the data obtained closest to the scheduled date will be used. If this does not eliminate duplication, data from the scheduled visit will be used. Unscheduled visits will not be included in the time-points for analysis. For the permitted ranges for the observation, test, and evaluation time-points shown in the study protocol, refer to Appendix 2.

For the final evaluation, data obtained at weeks 51 to 52 or at discontinuation of the treatment/tapering period will be used, except for CDRS-R and CGI-S scores, for which those obtained at week 50 or at discontinuation of the treatment period are used. However, if none of the above data are available, the latest data among reported data collected at scheduled visits are used for the final evaluation.

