10.5 Analysis of Columbia suicide severity rating scale

Columbia Suicide Severity Rating Scale (C-SSRS) will be analyzed. The time-points for evaluation of C-SSRS are taken to be the screening period and all scheduled visits during the treatment period, and the final evaluation time (weeks 51-52 or at discontinuation of the treatment period or tapering period).

- 1) The distribution of categories (yes, no) on the below evaluation scale will be summarized in the form of a shift table before and after administration initiation as well as before administration initiation and the final evaluation time (weeks 51-52, or at discontinuation of the treatment period or tapering period). For categories before administration initiation, subjects with at least one “yes” assessment at any one evaluation time-point in the screening period or before administration initiation will be classified as “yes”, and other subjects will be classified as “no”. For categories

after administration initiation, subjects with at least one “yes” assessment at any one evaluation time-point after administration initiation will be classified as “yes”, and other subjects will be classified as “no”. Both before and after administration initiation as well as the final evaluation time, subjects with missing observed values at all evaluation time-points will be classified as “non-assessed subjects”.

- 2) The number and proportion of subjects in each category at each evaluation time-point will be determined.

Columbia suicide severity rating scale	
Suicidal ideation	1. Wish to be dead 2. Non-specific Active suicidal thoughts.
Suicidal behavior	1. Actual attempt 2. Non-Suicidal Self-Injurious Behavior 3. Self-Injurious Behavior, intent unknown 4. Interrupted attempt 5. Aborted attempt 6. Preparatory Act or Behavior 7. Suicidal behavior 8. Completed suicide

- 3) For the following five questions about suicidal ideation, the distribution on the highest question number with at least one “yes” answer will be summarized in the form of a shift table of before versus after administration initiation.

Question No.	Questions
1	Wish to be dead
2	Non-specific Active suicidal thoughts.
3	Active suicidal ideation with any methods (not plans) but without intent to act
4	Active suicidal ideation with some intent to act, without specific plan
5	Active suicidal ideation with specific plan and intent

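### The visit-window rule has no exemption for ever-'yes' and worst-category safety tables, so a sole C-SSRS 'yes' at an out-of-window mid-study visit would most naturally be tabulated as 'no'

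*Protocol*

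**What the plan says.** Protocol 7.9 ties all assessments to the visit schedule ("Examination, observation and tests will be performed in accordance with Appendix 1"), gives a permitted day range for each visit in Table 7-3, and then states: "Data collected outside the permitted range will be taken to be missing for that visit". C-SSRS and ECG are both in Appendix 1, and neither is exempted. Under Protocol 7.7.2 the C-SSRS is done at every visit through Visit 18.

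SAP 6.3 says that, in principle, data "collected in accordance with the performance schedule shown in the study protocol, will be used for the statistical analysis". It points to the same windows, repeated in SAP Appendix 2, and adds: "Unscheduled visits will not be included in the time-points for analysis". SAP 6.4 does not impute in principle.

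SAP 10.5 sets the C-SSRS time-points as screening, "all scheduled visits during the treatment period, and the final evaluation time". For the shift table in 10.5(1), a subject with at least one 'yes' "assessment at any one evaluation time-point after administration initiation will be classified as" 'yes', and all others are 'no'. The non-assessed category is kept for subjects missing at every time-point. SAP 10.4(1) takes the worst ECG category after first dose by a priority ranking.

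**The concern.** Windows do useful work in a table of means by visit, because they stop a Day 40 value being averaged with Day 28 values. An ever-'yes' or worst-category table asks something else: whether the finding occurred at any time after first dose. The day of collection has no bearing on that. If the window rule is carried into these tables, a genuine observation already in the case report form is dropped, and the subject moves to 'no' or 'normal' rather than to a visible missing category. A reader of the table could not tell.

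Long-term safety is the primary objective, and suicide-related events are the adverse events of special concern in Protocol 7.7.7.6. With a target of 135 registered subjects, a single reclassified case is noticeable.

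**Working it through.** **Inputs.** Target days and permitted ranges for Visits 3 to 17 come from Protocol Table 7-3 (the same in SAP Appendix 2). The classification rules come from SAP 10.4 and 10.5, and the target of 135 from Protocol 8.2.

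**Step 1: reproduce the plan's ranges.** Range = target day ± permitted days.
- Visit 3: 7 ± 3 = 4–10. Visit 4: 14 ± 3 = 11–17.
- Visit 5: 28 ± 7 = 21–35. Visit 6: 56 ± 7 = 49–63. The pattern repeats every 28 days to Visit 16: 336 ± 7 = 329–343.
- Visit 17: 350 ± 3 = 347–353.

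All 15 ranges agree with Table 7-3.

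**Step 2: the gaps.** Between consecutive visits from 5 to 16, the days in no window number 28 − 15 = 13 (36–48, 64–76, …, 316–328). There are eleven such gaps. Days 1–3, 18–20 and 344–346 are also outside every window.
- Covered: 7 + 7 + 12 × 15 + 7 = 201 days.
- Uncovered: 3 + 3 + 11 × 13 + 3 = 152 days.
- Check: 201 + 152 = 353, and 152/353 = 43.1%.

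**Step 3: follow one subject through the rules.** Visit 5 takes place on Day 40. That is 12 days after target, 5 days past the end of its window and 9 days before Visit 6's window opens. The C-SSRS is 'yes'. Every other visit is in window and 'no'.
1. Protocol 7.9: the Day 40 result is missing for Visit 5.
2. SAP 6.3: it was not collected to schedule, and it cannot enter as an unscheduled visit.
3. SAP 10.5(1): no remaining time-point is 'yes', so the subject is not 'yes'.
4. The subject has other observed time-points, so is not 'non-assessed'. The result is 'no'.

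**Step 4: ECG.** Before the final evaluation, SAP 10.4 has two post-dose ECG time-points, weeks 4 and 28. An abnormal ECG taken outside Days 21–35 or 189–203, with the other readings normal, leaves the worst category as normal. One out-of-window ECG removes half of the pre-final readings.

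**Step 5: size.** The documents give no visit-adherence figure, so this is illustration only. Let *p* be the share of subjects with exactly one post-dose 'yes', and *q* the chance that this visit is out of window. Expected number misclassified = 135 × *p* × *q*.
- *p* = 5%, *q* = 2%: 135 × 0.05 × 0.02 = 0.135.
- *p* = 20%, *q* = 10%: 135 × 0.20 × 0.10 = 2.7.

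**The case against.** The best reply is that the text need not be read this way. Protocol 7.9 makes the data missing for the visit, not for every analysis. SAP 6.3 speaks in principle, and it expressly uses the ranges to assign time-points only for discontinuation data. SAP 10.5 lists scheduled visits without a window condition, and a late Visit 5 is still a scheduled visit. This shows that the plan is ambiguous. It does not remove the problem: no sentence re-admits an out-of-window mid-study assessment to 10.5(1) or 10.4(1), and 10.5(1) is built on visit time-points. Items 10.5(3) and (4) ask for at least one 'yes' without naming evaluation time-points, so the C-SSRS tables could disagree about the same subject.

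Three further replies stand and limit the point.
- **Discontinuation visits.** A reader might infer that a C-SSRS done more than 3 days after the last treatment-period dose is lost. SAP 6.3 takes discontinuation data for the final evaluation and, failing those, the latest scheduled-visit data. Neither clause repeats the day limit, so such an assessment may well be recovered.
- **Adverse-event capture.** Protocol 7.7.2 records clinically significant C-SSRS changes as adverse events. These are not windowed and can appear in the Suicide/self-injury SMQ table (SAP 10.1(7)); clinically significant ECG changes are likewise adverse events. The backup is incomplete, because a 'yes' not judged significant has no such route, and Protocol 7.7.7.1 keeps non-serious changes in CDRS-R items, which include suicidal ideation, out of adverse-event reporting.
- **Direction of loss.** A reader might infer that worsening subjects attend late, so that the loss is selective. That is plausible, but nothing in the documents shows it.

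**Conclusion.** The point holds in a limited form. On the most natural reading, a sole C-SSRS 'yes' at an out-of-window mid-study scheduled visit, with in-window visits 'no', is tabulated 'no', and an abnormal ECG can be lost from the worst-category table in the same way. The practical loss is mainly a 'yes' that was not judged clinically significant.

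A reader might take the 43% of days outside any window as the share of data lost. It is not: it counts calendar days, whereas visits are planned for the window centres and Protocol 7.9 allows departures only for unavoidable reasons. Nor does the chance of losing at least one assessment measure misclassification. If each of 15 attended visits independently had a 2%, 5% or 10% chance of being out of window, 1 − (1 − *q*)^15 gives 26%, 54% or 79%, but a lost assessment changes the classification only if it held the subject's only 'yes'.

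The number affected is probably small: about 0.1 to 2.7 subjects under the assumed values, with true adherence unknown. The study is uncontrolled and these tables are descriptive, so no between-group comparison is distorted. The correction is still worth making, because the rule can give a wrong count in a table meant to show suicidality.

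**What to change.** In SAP 6.3, and in Protocol 7.9 if it is reopened, limit the out-of-window rule to summaries by visit. Then state that every C-SSRS and ECG assessment made after first dose at a scheduled or discontinuation visit, whatever the day, counts in the after-initiation ever-'yes' and worst-category tables: SAP 10.5(1), (3) and (4), and 10.4(1). Using the same sentence for all four also removes the difference in wording within 10.5. By-visit tables and the handling of unscheduled visits stay as they are.

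The cost is SAP wording and one programming condition, since the data are already in the case report form. The reported C-SSRS 'yes' count may be slightly higher. If the protocol is not amended, Protocol 8.1 already provides for changes to the planned analysis to be recorded in the SAP with the reason.

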8.1 Statistical analysis methods

The sponsor will commission a contract organization to perform the statistical analysis. The sponsor will perform the pharmacokinetic analysis. The details of the analysis will be stipulated in the “Statistical analysis plan” and “Pharmacokinetic analysis plan”, which will be prepared on the basis of this section. When any change is made to the analysis planned in the protocol, reason for a change will be specified in the statistical analysis plan or pharmacokinetic analysis plan without fail.

Number of subjects, arithmetic mean, standard deviation, minimum, median, and maximum will be calculated as summary statistics for the items measured by continuous data in principle. Number of subjects and proportion of each category will be calculated as summary statistics for the items measured by discrete value.

Level of significance at 0.05 (two-sided) will be used for statistical tests in this study unless otherwise specified. There will be no multiplicity adjustment for the statistical tests.

SAS of Version 9.2 or higher will be used for all analyses and for creation of tables.

8.2 Target number of subjects

The target number of subjects is set as at least 100 subjects to collect data from, who receive duloxetine for one year. Assuming that 25% of subjects dropout from this study, the target total number of registered subjects is 135, including consecutive subjects and new subjects. Blood samples for plasma drug concentration measurements will be collected five times for each subject to evaluate the pharmacokinetics in Japanese children and adolescent patients with depressive disorder.

8.3 Analysis sets

The following analysis sets are defined:

(1) Full-analysis set (FAS)

This comprises all subjects to whom the study drug has been administered at least once, and with whom the CDRS-R total score has been determined at baseline and at least once after initiation of study drug administration.

(2) Safety-analysis set

This comprises all subjects to whom the study drug is administered at least once.

(3) Pharmacokinetic analysis set

This comprises all subjects to whom the study drug is administered at least once and the plasma duloxetine concentration is measured at least once. The pharmacokinetic analysis set will be used for preparing and summarizing the list of drug concentrations.

8.4 Handling of missing data

In principle, missing data will not be imputed. However, if missing data is imputed for analysis at the final evaluation time point, LOCF may be used.

8.5 Subject characteristics

Of the subjects registered, the number and proportion who complete the study, and the number and proportion withdrawn will be summarized. In addition, the reasons for withdrawal will be summarized. The number and proportion of subjects included in each analysis set will also be shown.

8.6 Demographic and baseline characteristics

The summary statistics will be used to summarize the demographic and baseline characteristics of the safety analysis set.

8.7 Study drug administration period, dosage, and treatment compliance

The study drug administration period, administration rate, and total dose will be summarized on the safety analysis set.

8.8 Prior treatment

Drugs used in prior treatment will be coded for using the WHO Drug Dictionary. With the safety analysis set, the subjects who received prior treatment will be tabulated.

8.9 Concomitant treatment

Drugs used in concomitant treatment will be coded for using the WHO Drug Dictionary. For the safety analysis set, the subjects who receive concomitant therapy will be tabulated.

8.10 Analysis of efficacy

The summary statistics will be calculated using the FAS for the observed efficacy endpoints (CDRS-R total score and CGI-S) and their changes from baseline at each time-point after study drug administration. The baseline for each endpoint is defined as the subject's initiation of this study (Visit 2). Changes from the start of the preceding study will be summarized similarly by treatment group in the preceding study.

8.11 Safety analysis

Safety analysis will be conducted on the safety analysis sets.

8.11.1 Adverse events

Adverse events will be classified by system organ class and preferred term, in accordance with MedDRA. Of the adverse events reported using CRFs, TEAEs will be used for safety analysis. TEAEs are defined in Section 7.7.7.11 .

The number of subjects suffering TEAEs, and the numbers suffering death, other serious TEAEs, TEAEs leading to discontinuation of administration, and TEAEs leading to dose reduction will be determined. The TEAE rate and 95% confidence interval will be calculated by the Clopper-Pearson method. The number

of adverse events will also be included. Adverse drug reactions will be summarized in the same manner as TEAEs. Adverse drug reactions are defined in Section 7.7.7.4 .

As summarization of TEAEs by system organ class and preferred term, the number and proportion of subjects suffering these events will be shown. In addition, TEAEs will be summarized by severity, onset timing, and outcome. Adverse drug reactions will be summarized similarly.

8.11.2 Blood pressure, pulse rate, and body weight

Summary statistics will be calculated for the measurements and change from baseline at each time-point. The baseline is defined as the subject's initiation of this study (Visit 2).

8.11.3 Laboratory test results

Summary statistics will be calculated for the measurements and change from baseline at each time-point.

The baseline is defined as Visit 1 for new subjects or Visit 2 for consecutive subjects.

The category distribution of the qualitative laboratory test data at each time-point will be summarized.

8.11.4 ECG

The distribution of ECG findings (normal or abnormal) will be summarized for observation time-point.

8.11.5 Columbia Suicide Severity Rating Scale (C-SSRS)

The distribution of the presence or absence of suicidal ideation and suicidal behavior will be summarized for observation time-point.

8.12 Pharmacokinetic analysis

Plasma duloxetine concentrations and time from the last administration will be listed for each subject. Trough plasma concentrations, which are 18 to 30 hours after the last administration of duloxetine, for each subject will be collected and summarized for each dose group by the number of subjects with measurements, arithmetic mean (Mean), standard deviation (SD), coefficient of variation (CV% = $SD/Mean \times 100$), median, minimum (Min), and maximum (Max). The plasma concentration below quantifiable limit will be substituted with 0. The plasma duloxetine concentrations at steady state from children and adolescent patients with depressive disorder will be compared with those of adult patients with depressive disorder. The relationship between the trough concentration of duloxetine and CDRS-R total score will be displayed in a graph.

Data considered by the pharmacokinetic analysts to be clearly inappropriate to include in the analysis will be excluded from the analysis. If excluded, the reason for exclusion shall be described in the clinical study report.

The population pharmacokinetic analysis will be conducted using a nonlinear mixed effect model, with NONMEM version 7.3 or higher. The report of population pharmacokinetic analysis will be prepared separately.

8.13 Interim analysis

After completing registration of subjects, once all subjects complete (or withdraw) observation at Visit 11 (Week 28), an interim analysis may be performed to assess the safety and efficacy of duloxetine administered for 6 months. The method of interim analysis should follow that of the analysis at the end of study.

9. Management-related items requiring attention

9.2 Institutional review board (IRB)

The IRB will protect the human rights, safety and welfare of subjects by reviewing study-related documents (including revised versions when any important amendments are made to these documents) such as the protocol, informed consent form and explanatory documents (or assent documents), materials

relating to subject recruitment (when applicable), other documents provided to subjects, the investigator's brochure, safety information, and annual reports of study performance (when applicable), as submitted by the principal investigator or sponsor. The IRB will be established on the basis of the GCP and various regulations. This study will be initiated after the principal investigator has obtained written approval by the IRB.

Revision of the protocol should be deliberated as done for the initial deliberation. The principal investigator will submit all periodic reports and updated information upon request by the IRB. The principal investigator will report all the applicable adverse events to the IRB.

9.3 Ethics

The clinical study will be performed in accordance with the appropriate regulatory requirements and the protocol approved by the IRB, and in compliance with the latest GCP, all appropriate requirements for protection of subjects' confidentiality, and ethical principles based on the Declaration of Helsinki.

